2.5.7 Other Options

The intrinsic apoptotic pathway is often dysregulated in relapsed CLL/SLL due to a deficiency in pro-apoptotic proteins such as TP53 and overexpression of anti-apoptotic proteins such as Bcl-2. ABT-199 is a selective, potent, orally bioavailable, small molecule Bcl-2 inhibitor that can trigger apoptosis. Seymour *et al.* looked at 56 patients who were enrolled with a median time on study of 10.0 months. ABT-199 showed activity in patients with relapsed/refractory CLL with a response rate of 84% including 20% CR and CR with incomplete marrow recovery (CRi). The most common adverse events (all grades involving 25% or greater patients) were diarrhea (46%), neutropenia (43%), fatigue (34%), upper respiratory tract infection (29%), and cough (25%). Grade 3 or 4 adverse events occurring in 4 or more patients were neutropenia (41%), TLS (11%), thrombocytopenia (10%), hyperglycemia (10%), anemia (7%), and febrile neutropenia

(7%). This study is continuing enrollment using a revised dosing schedule designed to reduce the identified risk of tumor lysis syndrome. A phase 2 monotherapy study in patients with relapsed CLL patients with deletion 17p has commenced as well as combination studies with either rituximab or obinutuzumab in patients with relapsed CLL.⁴⁷

2.6 Ibrutinib

2.6.1 Mechanism of Action, Distribution, Metabolism and Clearance⁴⁸

Ibrutinib (PCI-32765) is a covalent BTK inhibitor, which blocks BCR signaling and induces apoptosis of malignant B cells.⁴⁹ *In vitro*, ibrutinib forms a potent irreversible bond with cysteine-481 residue at the active site of BTK (IC₅₀ = 0.39 nM), and results in sustained inhibition of BTK catalytic activity and enhanced selectivity over other kinases that do not contain a cysteine at this position. When added directly to human whole blood, ibrutinib inhibits signal transduction from the BCR (IC₅₀ = 80 nM) as assayed by anti-IgM stimulation followed by CD69 expression.⁵⁰ In human B cells, ibrutinib blocked the transcriptional up-regulation of B-cell activation genes within 6 hours. 1-hour pulse exposure of ibrutinib followed by washout was sufficient to prevent up-regulation of these genes, indicating that ibrutinib acts as an irreversible inhibitor of the BCR pathway.⁵¹

The plasma protein bindings of ibrutinib and PCI-45227 are 97.3% and 91.0%, respectively. The apparent steady-state volume of distribution (V_{dss}/F) is approximately 10,000L (based on non-compartmental and population PK analyses), suggesting extensive distribution to peripheral tissues and/or binding to macromolecules in circulation. The blood-to-plasma ratio around T_{max} is approximately 0.7.

Following oral administration of ibrutinib at doses ranging of 420, 560, and 840 mg/day, exposure to ibrutinib increased as doses increased with substantial intersubject variability. The mean half-life (t_{1/2}) of ibrutinib across 3 clinical studies ranged from 4 to 9 hours, with a median time to maximum plasma concentration (T_{max}) of 2 hours. Taking into account the approximate doubling in mean systemic exposure when dosed with food and the favorable safety profile, ibrutinib can be dosed with or without food. Ibrutinib is extensively metabolized primarily by cytochrome P450 (CYP) 3A4. The on-target effects of metabolite PCI-45227 are not considered clinically relevant. Steady-state exposure of ibrutinib and PCI-45227 was less than 2-fold of first dose exposure. Less than 1% of ibrutinib is excreted renally. Ibrutinib exposure is not altered in patients with creatinine clearance (CrCl) >30 mL/min. Patients with severe renal impairment or patients on dialysis have not been studied. Following single dose administration, the AUC of ibrutinib increased 2.7-, 8.2- and 9.8-fold in subjects with mild (Child-Pugh class A), moderate (Child-Pugh class B), and severe (Child-Pugh class C) hepatic impairment compared to subjects with normal liver function. A higher proportion of Grade 3 or higher adverse reactions were reported in patients with B-cell malignancies (CLL, MCL and WM) with mild hepatic impairment based on NCI organ dysfunction working group (NCI-ODWG) criteria for hepatic dysfunction compared to patients with normal hepatic function.

Excretion is predominantly via feces (approximately 80% recovered within 2 days), and less via urine (~8%). The apparent clearance in subjects with B-cell malignancies is high: in the order of 1000 L/h. The half-life of ibrutinib is 4-6 hours. Overall, these pharmacokinetic (PK) characteristics resulted in minimal accumulation of both parent compounds and metabolite PCI-45227 on repeated daily dosing of ibrutinib. Steady-state exposure of ibrutinib and PCI-45227 was less than 2-fold of first dose exposure.

2.6.2 Clinical Experience in CLL

Once-daily administration of ibrutinib causes sustained inactivation of BTK resulting inhibition of BCR signaling and tumor microenvironment interactions.^{52,53} ENREF 53 The phase 1b/2 multicenter ibrutinib trial reported by Byrd *et al.* involved 85 relapsed CLL patients where 51 received 420 mg, and 34 received 840 mg.^{54,55} ORRs were 71% in both dosing groups, with an additional 15-20% had a partial response with lymphocytosis (PR-L). At 26 months, the estimated PFS was 75%, and OS was 83%. A single-agent

ibrutinib was overall well tolerated, while commonly observed side effects included thrombocytopenia, diarrhea, bruising, neutropenia, anemia, upper respiratory tract infection, fatigue, musculoskeletal pain, rash, fever, constipation, peripheral edema, arthralgia, nausea, stomatitis, sinusitis and dizziness. When ibrutinib was compared to ofatumumab in 391 previously treated CLL in a randomized phase 3 study, ibrutinib achieved significantly higher ORR (42.6% vs. 4.1%, $p < .001$) and showed survival benefit (12-month OS: 90% vs. 91%, hazard ratio 0.43, $p = .005$).⁵⁵

Responses to ibrutinib appear to be independent of clinical and genomic risk factors. In the elderly CLL population of age 65 years or older, ibrutinib was a well-tolerated initial therapy, and led to ORR of 71% (13% had CR; 3% had nodal PR, 55% ad PR).⁵⁶ In the high-risk CLL population with *TP53* mutation, a ibrutinib was an active single-agent treatment as an initial therapy as well as for relapsed or refractory CLL, and led to ORR of 97% (55% had PR; 42% had PR-L).⁵⁷

In July 2014, ibrutinib received a full approval in the US for CLL patients who have received at least one prior therapy, and for the patients with 17p deletion. Response to ibrutinib appears to be independent of clinical and genomic risk factors, and it currently stands as the sole FDA-approved agent with the treatment indication for CLL with 17p deletion. Long-term data regarding responses and toxicity are still maturing for ibrutinib. Notably, a 3-year post-initiation data of 132 previously untreated and relapsed/refractory CLL patients on ibrutinib did not show new safety signal.⁵⁸ The observed median duration of response was not reached for all treated patients on study, while it was 25 months for the subset with deletion 17p. 30-month PFS was 96% among patients who received ibrutinib as a frontline.⁵⁹

Ibrutinib has been investigated in combinations with other agents including chemoimmunotherapies in CLL, and early experiences were reported to date. Barrientos *et al.* reported on 30 patients with relapsed/refractory CLL/SLL that received up to 6 cycles of BR with a continuous fixed ibrutinib dose of 420 mg/day.⁶⁰ With the median treatment duration of 16 months, the ORR was 93% (28/30 patients, including 5 CRs and 3 nodal PRs), and one additional patient achieved a PR-L. The estimated 12 month PFS was 90%, and the responses appeared to be independent of high-risk features. The most frequently reported adverse events were diarrhea (70%), nausea (66.7%), fatigue (46.7%), neutropenia (40%) and upper respiratory tract infection (36.7%). Adverse events in grade 3 or higher in severity included neutropenia (40%), maculopapular rash and fatigue (10% each), and thrombocytopenia, febrile neutropenia, and cellulitis (6.7% each).

Ibrutinib in combination with rituximab was investigated in two different phase II trials. The first study reported 40 high-risk CLL patients who were treated with daily ibrutinib and 6 cycles of rituximab.⁶¹ At the median follow up of 14 months, 32 of 40 patients continue on therapy without disease progression. Based on 2008 IWCLL guideline, ORR was 95% (87% in PR; 8% in CR), and one patient in CR achieved minimal residual disease negativity by flow cytometry. Notably, the response rate of patients with 17p deletion or *TP53* mutation was 90%, with the majority of them achieving PR. Treatment generally was well tolerated, with infectious complications being the most common adverse event. 8 patients came off study; 3 patients died from unrelated infectious complications (2 cases of sepsis, 1 case of pneumonia), 1 died from unrelated respiratory and cardiovascular failure, 2 came off study due to possible ibrutinib-related toxicity (one subdural hematoma, one grade 3 mucositis), 1 had progressive disease, and 1 proceeded to stem cell transplantation. The second study randomly assigned 93 relapsed CLL patients to either ibrutinib alone or ibrutinib and rituximab, and reported more rapid abrogation of lymphocytosis in the combination arm.⁶²

Byrd *et al.* reported on ibrutinib in combination with ofatumumab for treatment of relapsed CLL/SLL. For the 27 enrolled CLL/SLL patients, ORR defined by IWCLL criteria was 100%, PFS was 100% at the median follow-up of 9.8 months.⁶³ 89% of CLL/SLL/prolymphocytic leukemia (PLL) patients remain on study and only one patient has discontinued treatment by proceeding to stem cell transplant. The majority of adverse events were grades 1 or 2, and no grade 3 or 4 infusion reactions, neutropenia, or thrombocytopenia have been observed.

Limitations of ibrutinib have been identified as clinical experiences are accumulating. First, deep responses with a single-agent ibrutinib are rare. When ibrutinib was combined with other agents, CR rate increased to 8% (ibrutinib/rituximab)⁶¹ and 16% (ibrutinib plus BR),⁶⁴ which still fall short of conventional approaches.^{34,35} Second, acquired mutations in BTK and in phospholipase C-gamma 2 (PLCγ2), a direct downstream target of BTK, were identified in six CLL patients who developed secondary resistance to ibrutinib.^{65,66} Among them, five showed a cysteine-to-serine mutation in BTK (C481S), which disrupts the covalent binding between the drug and the kinase, and thereby dramatically decreases the potency of ibrutinib. Two patients, including one with C481S mutation, had gain-of-function mutations in PLCγ2 leading to autonomous BCR signaling.⁶⁵

2.7 Summary of Clinical Safety

A brief summary of safety data from monotherapy and combination therapy studies is provided in below. For more comprehensive safety information please refer to the current version of the IB. Additional safety information may be available for approved indications in regional prescribing labels where the study is conducted.

For monotherapy studies:

Pooled safety data for a total of 1318 subjects treated with ibrutinib monotherapy in 13 studies that have completed primary analysis or final analysis as of the 31 May 2016 cutoff date for the current IB update in B-cell malignancies are summarized below.

Most frequently reported treatment-emergent adverse events (TEAEs) in subjects receiving ibrutinib as monotherapy (N=1318):

Most frequently reported TEAEs ≥ 15% ^a	Most frequently reported Grade 3 or 4 TEAEs ≥ 3% ^b	Most frequently reported Serious TEAEs ≥ 2% ^c
Diarrhea	Neutropenia	Pneumonia
Fatigue	Pneumonia	Atrial fibrillation
Nausea	Thrombocytopenia	Febrile neutropenia
Cough	Anemia	Pyrexia
Anemia	Hypertension	
Pyrexia	Diarrhea	
Neutropenia	Atrial fibrillation	
Upper respiratory tract infection		
Thrombocytopenia		
Edema peripheral		

^a Source is Table 6 of IB (v11), ^b Source is Table 8 of IB (v11), ^c Source is Table 9 of IB (v11).

Rarely, in less than 1% of cases, pneumonia was attributed to the infection of *Pneumocystis jirovecii*. Most cases of *Pneumocystis pneumonia* (PCP) were reported as a single case from different monotherapy and combination studies.

For combination therapy studies:

Pooled safety data for a total of 423 subjects treated with various therapies in combination with ibrutinib from 4 studies conducted in B-cell malignancies, which included 1 randomized-control study, are summarized below. Therapies used in combination with ibrutinib in these studies, included BR (bendamustine and rituximab), FCR (fludarabine, cyclophosphamide, and rituximab), ofatumumab, and R-CHOP (rituximab, cyclophosphamide, doxorubicin, vincristine, and prednisone).

Most frequently reported TEAEs in subjects receiving ibrutinib in combination therapy (N=423):

Most frequently reported TEAEs $\geq 20\%$ ^a	Most frequently reported Grade 3 or 4 TEAEs $\geq 3\%$ ^b	Most frequently reported Serious TEAEs $\geq 2\%$ ^c
Neutropenia	Neutropenia	Febrile neutropenia
Diarrhea	Thrombocytopenia	Pneumonia
Nausea	Febrile neutropenia	Atrial fibrillation
Thrombocytopenia	Pneumonia	Pyrexia
Fatigue	Hypertension	Cellulitis
Anemia	Neutrophil count decreased	
Pyrexia	Anemia	
	Fatigue	
	Diarrhea	

^a Source is Table 10 of IB (v11), ^b Source is Table 12 of IB (v11), ^c Source is Table 13 of IB (v11).

Rarely, in less than 1% of cases, pneumonia was attributed to the infection of *Pneumocystis jirovecii*. Most cases of Pneumocystis pneumonia (PCP) were reported as a single case from different monotherapy and combination studies.

2.7.1 Clinical and scientific justification for protocol design

Combinations of chemoimmunotherapies as front-line CLL treatment have significantly improved patient outcomes. Nevertheless, approximately 10% of CLL patients do not respond to fludarabine-based therapies and approximately half eventually progresses with relapsed or refractory diseases. Chemoimmunotherapies also leads to short- and long-term toxicities. These limitations call for a novel treatment approach that is both efficacious and safe.

BCR signaling, a pathway critical for malignant B-cell activation, is pharmacologically targetable. Inhibition of BTK with ibrutinib was proven to be effective and well tolerated in CLL,⁵² leading to FDA-approval of ibrutinib for CLL patients who had at least one prior treatment or CLL with deletion 17p. The use of ibrutinib upfront is justified in patients with deletion 17p, and the proposed combination of ibrutinib and fludarabine may be particularly desirable in this patient population.

Along with the accumulation of clinical experiences, a single-agent ibrutinib is identified to have several limitations. First, deep responses are infrequent. CR was seen in only 2% of relapsed or refractory CLL⁵⁴ and in 13% of treatment-naïve CLL.⁵⁶ When ibrutinib was combined with other agents, CR rate increased to 8% (ibrutinib/rituximab)⁶⁷ and 16% (ibrutinib/bendamustine/rituximab),⁶⁴ which still fall short of conventional approaches.^{34,35} Moreover, acquired mutations in BTK and phospholipase C-gamma 2 (PLC γ 2), a direct downstream target of BTK, were identified in 6 CLL patients who developed secondary resistance to ibrutinib.^{65,66} Among them, five showed a cysteine-to-serine mutation in BTK (C481S), which disrupts the covalent binding between the drug and the kinase, thereby dramatically decreasing the potency of ibrutinib.⁶⁵ We hypothesize that the addition of a second agent could augment the depth of response and prevent drug resistance. This constitutes one rationale for the trial design.

Notably, T-cells in CLL are capable of stimulating tumor cells and promoting resistance to apoptosis through CD40 ligand and other pathways.^{9,10} *In vivo*, T-cells and CLL cells were shown to aggregate and form ‘proliferation centers’ within bone marrow and lymphoid tissues, and these rallied cells were necessary for CLL cell proliferation.⁶⁸ Using fludarabine as the second agent provides a mean to target these T-cells.

In this context, immunotherapy is an attractive option for long-term disease control. Allogeneic stem cell transplantation set the paradigm of a curative approach using immune reconstitution; however, it is only available for a minority of patients. The clinical successes with chimeric antigen-receptor (CAR) T cells provide a strategy for more general application of T-cell immunotherapy in CLL. However, T-cells in CLL

are functionally⁶⁹ and phenotypically¹¹ defective, or “pseudo-exhausted”, due to inhibitory signals from leukemic B cells - such as CD200, PD-L1 and B7-H3⁸ - and these signals appear to reduce the efficacy of CAR T cells. Fludarabine has been used successfully as a preparative agent before immunotherapies and can promote reconstitution of the T-cell compartment through homeostatic proliferation.⁷⁰

Thus, we view CLL as a clonal proliferation of auto-reactive B-cells that escape immune surveillance, and are stimulated through BCR signaling and T-cell interaction. We propose to combine ibrutinib with a short-course fludarabine to achieve two goals: first, eliminate or greatly decrease T-cell help towards CLL cells; and second, replace the dysfunctional T-cell population. Fludarabine, a purine analog cytotoxic to both B and T cells,^{32,72,73} is a biologically plausible addition to ibrutinib with a large body of experience in CLL treatment.^{32,34,71} In addition, fludarabine is frequently used as a part of conditioning regimen during hematopoietic stem cell transplant^{72,73} and adoptive cell transfer^{74,75} with an aim to deplete lymphocytes and reconstitute immune microenvironment. Preclinical and clinical evidences support the immune modulatory role of fludarabine and subsequent recovery of T cells in CLL. Notably, reconstitution of CD4+ T, CD8+ T, and NK cells were demonstrated in CLL after treatment with fludarabine.⁷⁰ Regulatory T cells decreased after fludarabine exposure.⁷⁶

[figure not shown]
We hypothesize that recovering T-cell populations after a short-course fludarabine will have an improved functional capacity, and can exert anti-leukemic effects by the recovery of immune surveillance function. We consider the combination of ibrutinib and fludarabine as a possible platform to which immune therapeutic approaches, such as vaccines, CAR T-cells, or checkpoint inhibitors, may be added in subsequent steps. In this study, we will investigate the effect of the combination therapy on the depth of response and on the composition of the T-cell compartment. We will compare the correlative data to our experience with single-agent ibrutinib in over 70 patients, and the ongoing study using fludarabine, cyclophosphamide, and ofatumumab in previously untreated CLL patients.

The following specific issues have been considered in the study design:

- Studying untreated CLL/SLL is justifiable as the side effect profile of ibrutinib is favorable and fludarabine is the current standard front-line agent.
- The combination of ibrutinib and chemotherapy has been well tolerated⁶⁴ and there are ongoing clinical trials combining ibrutinib with chemoimmunotherapies, including a phase III study of BR plus ibrutinib (NCT01611090), a phase II study of FCR plus ibrutinib (NCT02251548), and a phase III study with an arm for ibrutinib plus rituximab (NCT02048813).

3.0 STUDY DESIGN

This is a phase II single center trial. It is a prospective, single-arm, open-label study of ibrutinib and a short-course fludarabine in previously untreated subjects with CLL or SLL. Each cycle is 28 days. Patients will initiate ibrutinib first for cycle 1 and 2, followed by the addition of short-course fludarabine for cycle 3 and 4. Ibrutinib will be given continuously until disease progression or intolerable side effects.

4.0 ELIGIBILITY ASSESSMENT AND ENROLLMENT

4.1 Inclusion Criteria

1. Men and women with histologically confirmed disease as defined by the following:
 - CLL: clonal B-lymphocytosis $\geq 5,000$ cells/ μ L .
 - SLL: lymphadenopathy with the tissue morphology of CLL but that are not leukemic, $< 5,000$ cells/ μ L.
 - Immunophenotypic profile or immunohistochemistry read by an expert pathologist as consistent with CLL. This will include CD5, CD19, and CD20 expression by the CLL cells typically also with CD23 expression, but CD23 negative cases may be included if there is an absence of t (11;14)
2. Active disease as defined by at least one of the following (IWCLL consensus criteria):
 - Weight loss $\geq 10\%$ within the previous 6 months
 - Extreme fatigue
 - Fevers of greater than 100.5°F for ≥ 2 weeks without evidence of infection
 - Night sweats for more than one month without evidence of infection
 - Evidence of progressive marrow failure as manifested by the development of, or worsening of, anemia and/or thrombocytopenia
 - Massive or progressive splenomegaly
 - Massive nodes or clusters or progressive lymphadenopathy
 - Progressive lymphocytosis with an increase of $>50\%$ over a 2-month period, or an anticipated doubling time of less than 6 months
3. Treatment naïve CLL/SLL patients
 - Treatment-naïve CLL indicates no prior anti-CLL therapy. Anti-CLL therapy includes chemotherapies, monoclonal antibodies, and targeted agents with known or reasonably expected anti-leukemic activity.
4. Eastern Cooperative Oncology Group (ECOG) performance status of ≤ 2
5. ANC $> 750/uL$, platelets $> 50,000/uL$
6. Agreement to use acceptable methods of contraception during the study and for 90 days after the last dose of study drug if sexually active and able to bear or beget children
 - Female subjects who are of non-reproductive potential (i.e., post-menopausal by history - no menses for ≥ 1 year; OR history of hysterectomy; OR history of bilateral tubal ligation; OR history of bilateral oophorectomy). Female subjects of childbearing potential must have a negative serum pregnancy test upon study entry.
 - Male and female subjects who agree to use both a highly effective method of birth control (e.g., implants, injectables, combined oral contraceptives, some intrauterine devices, complete abstinence, or sterilized partner) and a barrier method (e.g. condoms, vaginal ring, sponge, etc.) during the period of therapy and for 90 days after the last dose of study drug
 - Complete abstinence is a highly effective method only if defined as refraining from heterosexual intercourse during the entire period of risk associated with the study treatments. The reliability of sexual abstinence needs to be evaluated in relation to the duration of the clinical trial and the preferred and usual lifestyle of the subject.
7. Willing and able to participate in all required evaluations and procedures in this study protocol including swallowing capsules without difficulty
8. Ability to understand the purpose and risks of the study and provide signed and dated informed consent and authorization to use protected health information (in accordance with national and local subject privacy regulations)

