2.4 Indications for CLL Treatment

Newly diagnosed patients with asymptomatic early-stage disease (Rai 0, Binet A) should be monitored without therapy unless they have evidence of disease progression.³⁰ Patients with intermediate to high Rai stages (3 and 4) or Binet stages (B and C) usually benefit from treatment.

According to the International Workshop on Chronic Lymphocytic Leukemia (IWCLL), active disease should meet one of the following criteria.³

- Evidence of progressive marrow failure as manifested by the development of, or worsening of, anemia and/or thrombocytopenia
- Massive (i.e., at least 6 cm below the left costal margin) or progressive or symptomatic splenomegaly
- Massive (i.e., at least 10 cm in longest diameter) or progressive or symptomatic lymphadenopathy
- Progressive lymphocytosis with an increase of more than 50% over a 2-month period or LDT of less than 6 months. LDT can be obtained by linear regression extrapolation of absolute lymphocyte counts obtained at intervals of 2 weeks over an observation period of 2 to 3 months. In patients with initial blood lymphocyte counts of less than $30 \times 10^9/L$ ($30\,000/\mu L$), LDT should not be used as a single parameter to define a treatment indication. In addition, factors contributing to lymphocytosis or lymphadenopathy other than CLL (eg, infections) should be excluded.
- Autoimmune anemia and/or thrombocytopenia that is poorly responsive to corticosteroids or other standard therapy
- Constitutional symptoms, defined as any one or more of the following disease-related symptoms or signs:
 - a. Unintentional weight loss of 10% or more within the previous 6 months;
 - b. Significant fatigue (i.e., ECOG PS 2 or worse; inability to work or perform usual activities);
 - c. Fevers higher than $100.5^\circ F$ or $38.0^\circ C$ for 2 or more weeks without other evidence of infection; or
 - d. Night sweats for more than 1 month without evidence of infection.

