2.5 Current Treatment options for CLL/SLL

2.5.1 Watchful Waiting

Immediate treatment is recommended in patients with advanced-stage disease, high tumor burden, and severe disease-related "B" symptoms. Otherwise, a period of observation is recommended. Asymptomatic early-stage disease should be monitored until disease progression.³ During the observation period, patients are periodically monitored with blood counts and assessed for the evidence of progressive disease through monitoring of symptoms and physical exam.

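### Section 4.1 lets a doubling time under 6 months qualify a patient on its own at any lymphocyte count, while the IWCLL criterion set out in section 2.4 does not accept that below 30 x 10^9/L

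*Combined protocol and SAP*

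**What the plan says.** Section 4.1, item 2, requires "Active disease as defined by at least one of the following (IWCLL consensus criteria") and then lists the bullets. The lymphocytosis bullet has two arms: "Progressive lymphocytosis with an increase of $>50\%$ over a 2-month period, or an anticipated doubling time of less than 6 months". Neither arm carries a count condition. The only lymphocyte threshold in eligibility is in item 1, "CLL: clonal B-lymphocytosis $\geq 5,000$ cells/ μ L", which separates CLL from SLL.

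Section 2.4 sets out the IWCLL definition of active disease, including the same two-arm criterion, and adds two limits. The first, "LDT should not be used as a single parameter to define a treatment indication", applies to patients whose initial count is below 30 x 10^9/L. The second deals with causes of a rise that are not the leukaemia: "factors contributing to lymphocytosis or lymphadenopathy other than CLL (eg, infections) should be excluded".

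On patients without active disease, section 2.5.1 says: "Asymptomatic early-stage disease should be monitored until disease progression". Section 10.0 gives as the reason for DSMB review that ibrutinib and fludarabine have not been combined in a trial before.

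**The concern.** A person checking eligibility works from section 4.1. The list there is worded as a complete definition, and one bullet is enough. It keeps qualifiers where they were wanted: the fever and night-sweat bullets exclude infection, but the lymphocytosis bullet has no qualifier. Followed literally, it admits a patient whose only feature is a projected doubling time at a low count. Section 2.4 says that this alone does not define a treatment indication.

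The first stake is exposure. Such a subject would start continuous ibrutinib and receive two cycles of fludarabine in a new combination, without an indication by the protocol's own description.

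The second is interpretation. The trial is single-arm and tests the CR rate against a fixed 5%, so nothing in the design adjusts for case mix. The plan does not ask for the qualifying criterion to be recorded, so a reader could not later see how many subjects entered by this route.

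**Working it through.** **1. The sections side by side**

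| Element | 4.1 item 2 | 2.4 |
|---|---|---|
| Source named | IWCLL | IWCLL |
| Rise >50% in 2 months | sufficient, any count | sufficient, any count |
| Doubling time <6 months | sufficient, any count | not as single parameter if initial count <30 x 10^9/L |
| Other contributors to lymphocytosis | not mentioned in the bullet | to be excluded |

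The rest of 4.1, section 4.2, the screening and baseline lists in 6.1 and the schedule in Appendix A contain no 30 x 10^9/L condition.

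**2. Which patients are affected**

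The limit in 2.4 covers doubling time only. With exponential growth, a 50% rise in 2 months corresponds to a doubling time of 2 x ln 2 / ln 1.5 = 3.42 months. Patients growing faster than that qualify through the other arm in both sections.

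The disputed group therefore has doubling times of about 3.4 to 6 months, an initial count of 5 to 30 x 10^9/L, and no other bullet met. For example, at 10 x 10^9/L with a 5-month doubling time, the 2-month rise is 2^(2/5) - 1 = 32%. That fails the 50% arm, and the patient enters on doubling time alone. (If growth is taken as linear in the count, the lower bound is 4 months instead of 3.4.)

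**3. The plan's own figures**

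Inputs from section 9.3: 13 then 14 subjects, stop if there is no CR in the first 13, reject if there are 4 or more CRs in 27, null 5%, alternative 20%.

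P(reject) = sum over x = 1 to 3 of P(X1 = x) P(X2 >= 4 - x), plus P(X1 >= 4), with X1 ~ Bin(13, p) and X2 ~ Bin(14, p).

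At p = 5%: 0.3512 x 0.0301 + 0.1109 x 0.1530 + 0.0214 x 0.5123 + 0.0031 = 0.0416.

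At p = 20% the result is 0.801. Both agree with the stated type I error of 0.05 and power of 80%.

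**4. Illustration of a case-mix effect**

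The documents give neither the number of such patients nor a CR rate by baseline count, so both are assumptions here. Let k of the 27 have CR rate q and the rest 5%, and repeat the calculation in step 3 with each stage's total as a sum of unequal Bernoulli variables. The ranges cover every split of the k patients between the stages.

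| k | q = 10% | q = 20% |
|---|---|---|
| 0 | 4.2% | 4.2% |
| 1 | 4.6-4.7% | 5.5-5.7% |
| 2 | 5.1-5.2% | 7.0-7.5% |
| 3 | 5.6-5.8% | 8.8-9.7% |
| 4 | 6.1-6.4% | 10.7-12.1% |

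**The case against.** **The label imports the limits.** Section 4.1 is plainly shorthand in places: the size definitions of massive nodes and spleen and the ECOG gloss on fatigue also appear only in 2.4. An experienced investigator may read the IWCLL label as bringing in the whole criterion. That is a fair reading, but the list is framed as the definition itself, and omitting a limit on sole use changes who qualifies, not just how a term is measured. The objection makes this a point to clarify; it does not remove it.

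**Non-CLL causes are partly covered.** Item 1 requires clonal B cells and an expert-read immunophenotype, and section 6.1 requires flow cytometry or immunohistochemistry showing CLL/SLL. A purely reactive lymphocytosis would fail. Infection contributing to a rise in a patient with true CLL is not excluded, so this gap is narrow but open.

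**Observation is not plainly the alternative.** Section 2.4 qualifies monitoring by evidence of progression, and section 2.3 links a doubling time under 12 months with a progressive course. This weakens any claim that every such patient belongs under observation. It does not alter the specific limit in 2.4.

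**Stronger readings that the documents do not support.** A reader might infer that 4.1 replaces a measured doubling time with a guessed one. It does not: 2.4 says "LDT can be obtained by linear regression extrapolation of absolute lymphocyte counts obtained at intervals of 2 weeks", which is itself a projection and permissive, and 2.3 accepts a projected value.

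A reader might also infer that these patients start close to CR and so inflate the CR rate. Table 4 also requires a normocellular marrow with under 30% lymphocytes and no B-lymphoid nodules, and section 6.3 makes the marrow biopsy after cycle 6 mandatory. Table 1 lists marrow lymphocytosis even at Rai stage 0. A low blood count does not establish low marrow or nodal burden.

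**Conclusion.** The mismatch between 4.1 and 2.4 is in the text, and nothing in the eligibility or screening sections restores the doubling-time limit. It affects a defined and probably small group: 5 to 30 x 10^9/L, doubling time about 3.4 to 6 months (assuming exponential growth), no other criterion met. It matters mainly because such subjects could be exposed to a new combination when the protocol's own account says that this feature alone is not an indication.

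The two-stage design is sound as calculated, with exact type I error 4.2% and power 80.1%. An effect on the CR test is possible but cannot be sized from the documents. The ranges of 4.6-6.4% and 5.5-12.1% rest entirely on the assumed 1 to 4 such patients and assumed CR rates of 10% and 20%. They show how sensitive the rule is and do not estimate a bias. Carrying over the limit would not close every low-count route either, since the 2-month arm stays open at any count in both sections.

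**What to change.** Reconcile the lymphocytosis bullet in 4.1 with section 2.4 in one of two ways:

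- carry the 2.4 limits (sole use of doubling time below 30 x 10^9/L, and exclusion of other contributors) into the bullet; or
- state and justify a deliberate departure, and no longer label that bullet as IWCLL.

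Which rule is clinically right is for the investigators to decide.

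In either case, add to the eligibility form the criterion or criteria each subject met and the baseline lymphocyte count, and report both with the CR rate so that it can be read against case mix.

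The cost is a sentence in an amendment and an addition to the eligibility form. The sample size of 27 and the decision rule do not change. If the limits are carried over, accrual may be slightly slower, because a few low-count patients would wait until they meet another criterion.
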